## **Study Protocol and Statistical Analysis Plan with Results**

A total of 69 patients with uncontrolled open-angle glaucoma were recruited at the George Washington University by two glaucoma attending professors. Research protocol approval was obtained from the institutional review board of George Washington University (Washington, DC, USA) under IRB #041, 310 and registered on ClinicalTrials.gov with identifier NCT01956942. Written informed consent was received from all patients, and the protocol followed the Declaration of Helsinki.

This study included all laser trabeculoplasty candidates with open-angle glaucoma on maximally tolerated medical therapy with the need for additional IOP lowering. Patients with end-stage, neovascular, uveitic, or angle closure glaucoma were excluded. In all, 38 patients were randomized to MLT and 31 patients to SLT via a random number generator protocol approved for up to 100 patients. All patients had only one eye included in the study. Patients were allocated to each group without any stratification based on prior characteristics via sealed numbers in a set sequence. Recruitment was concluded after a power analysis revealed an 80% power at a 0.05  $\alpha$  level detecting an average 2.99 mmHg or 16.19% decrease from baseline between the SLT and MLT groups. This level was determined based on prior studies defining a \$3 mmHg or \$20.0% decrease in IOP as a significant difference from baseline.11 Patients, physicians, and researchers were not blinded to the different laser treatments. Each of the two physicians performed both the laser treatments and all subsequent follow-ups for a particular patient.

The MLT group underwent 360° treatment with the IQ 577 nm™ yellow laser (Iridex Corporation, Mountain View, CA, USA) with laser applied to the pigmented trabecular meshwork in a confluent manner. The laser settings for MLT were 1,000 mW, 300 ms duration, 300 µm spot size, and a 15% duty cycle. The SLT group received 360° treatment with the 532 nm Q-switched, frequencydoubled Nd:YAG Selecta II™ (Lumenis Inc, San Jose, CA, USA). The energy for SLT was titrated, between ~0.6 and ~2.0 mJ, based on trabecular meshwork pigmentation to achieve a noticeable gas bubble response, utilizing a 400 µm spot size and a 3 ns duration.

All patients were treated with one drop of apraclonidine prior to the treatment. Patients were discharged with topical diclofenac 0.1% to use as needed for discomfort. At week 1, patients completed a standardized survey querying discomfort experienced both during and after the procedure and use of the topical diclofenac.

Patients' IOP was measured at predefined intervals of 1 hour and 1-, 6-, 6–12-, 12–24-, 24–36-, and 36–52-week intervals based on a fixed follow-up of 1 and 6 weeks and a tendency to follow these patients every 3–4 months thereafter. Pretreatment IOP values were calculated as the average of up to three preceding visits to reduce fluctuations. Only the preceding visits without the addition of a drop or a laser were included to avoid confounding influences. If patients were examined multiple times within an interval, IOP values were averaged for statistical analysis. Patients' responses were excluded from the analysis if they underwent any interventions that may affect their IOP, including the addition of a topical antihypertensive drop, cataract surgery, cyclophotocoagulation, incisional glaucoma surgery, or further laser trabeculoplasty. However, their data were still included for the intervals up to the time of these interventions. Comparison between groups was calculated with Student's *t*-test for continuous data and a two-tailed Fisher's exact test for categorical data.

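### The arm comparisons leave out the treating physician: the tests remain valid overall, but a two-level physician term would cheaply remove any shift due to chance imbalance

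*Combined protocol and SAP*

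**What the plan says.** The opening section of the combined protocol and SAP (*Study Protocol and Statistical Analysis Plan with Results*) gives the design facts. Two glaucoma physicians recruited all 69 patients, and "38 patients were randomized to MLT and 31 patients to SLT via a random number generator protocol approved for up to 100 patients". On allocation it says: "Patients were allocated to each group without any stratification based on prior characteristics". On masking: "Patients, physicians, and researchers were not blinded to the different laser treatments". On who did what: "Each of the two physicians performed both the laser treatments and all subsequent follow-ups for a particular patient".

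The analysis is set out in the same section: "Comparison between groups was calculated with Student's" t-test for continuous data, with a two-tailed Fisher's exact test for categorical data. The *Results* section adds a log-rank P of 0.31 for time to failure. No physician covariate or stratum is mentioned for any of these.

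Failure is the need for further glaucoma treatment within 52 weeks. No criterion for that need is given. Patients who received further treatment are left out of the IOP analysis from then on.

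**The concern.** Each patient belongs to one physician for both treatment and follow-up, so a difference between the physicians could affect the outcome in several ways:

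- SLT energy was titrated to a visible response, which is an operator's judgement.
- A physician's threshold for further treatment plausibly affects the failure count. Because later IOP values are dropped after such treatment, it also affects which patients enter the later t-tests.

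Unstratified allocation of 69 patients does not guarantee that the two physicians are evenly represented in the arms. If they differ and the split was uneven, part of the observed arm difference reflects who treated whom. The available text gives no counts by physician and arm, so a reader cannot tell whether this happened. It matters somewhat here because the report concludes that the two lasers are comparable and sets its confidence intervals against 3 mmHg.

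**Working it through.** **Inputs from the document:** 38 MLT and 31 SLT patients; two physicians; 80% power at α = 0.05 for 2.99 mmHg; failures of 23.7% (9/38) and 12.9% (4/31). **Assumed, because the document gives neither:** the share of patients per physician (50:50 unless stated) and the physician difference D in IOP change (0 to 3 mmHg).

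**1. The plan's own figure.** "a power analysis revealed an 80% power at a 0.05" α level, but no SD is stated, so the 80% cannot be checked independently. Solving backwards:

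- √(1/38 + 1/31) = 0.2420
- SD = 2.99 / [(1.960 + 0.842) × 0.2420] = 4.41 mmHg (4.35 with the t distribution), two-sided
- implied SE of the arm difference = 4.41 × 0.2420 = 1.07 mmHg

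**2. Size of chance imbalance.** For a 50:50 split, the between-arm difference in one physician's share has SE = √[0.25 × (1/38 + 1/31)] = 0.121, or 12.1 percentage points. The exact hypergeometric calculation also gives about 12 points, with a 95% limit of about 25. With a 90:10 split these become about 7 and 13 points.

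**3. Shift in the arm difference** = D × imbalance:

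| D (mmHg) | 1 SE imbalance | 2 SE imbalance | As a fraction of the SE of 1.07 |
|---|---|---|---|
| 0 | 0 | 0 | 0 |
| 1 | 0.12 | 0.24 | 0.11–0.23 |
| 2 | 0.24 | 0.48 | 0.23–0.45 |
| 3 | 0.36 | 0.73 | 0.34–0.68 |

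**4. Overall error rate.** In simulation with a within-physician SD of 4.41 and D from 0 to 2 mmHg, the unadjusted t-test rejects a true null in 4.9% to 5.2% of runs. Power at 2.99 mmHg with a 50:50 split:

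- D = 1: 78.1% unadjusted, 78.3% adjusted
- D = 2: 76.9% unadjusted, 78.5% adjusted

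**5. Error rate given a large imbalance.** An imbalance of 20 points or more arises in about 9% to 11% of randomisations. Among those, the unadjusted type I error is 5.3% to 5.7% for D = 1 and about 7% for D = 2. A linear model with physician is valid given the imbalance that occurred, so it stays near the nominal 5%.

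**6. Price and gain of the physician term.**

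- If the physicians are alike, the expected squared correlation of arm with physician is 1/68 = 1.5%. This raises the SE by about half of that, 0.7%.
- If they differ, the unadjusted variance gains D²/4. For D = 2, √(4.41² + 1) = 4.52, and 4.41/4.52 × 1.007 = 0.98, an SE about 2% smaller. For D = 3, √(4.41² + 2.25) = 4.66, and 4.41/4.66 × 1.007 = 0.95, about 5% smaller.

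**The case against.** The strongest reply is that chance imbalance in any covariate is part of random error, and the unadjusted SE already allows for it. That is correct, and step 4 bears it out. A reader might infer that the arm comparison is biased or that physician is confounded with arm. The document does not support this: allocation was by random numbers, and nothing ties a physician to a laser.

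A second tempting reading is that physician imbalance could account for up to half of the failure difference of 23.7% − 12.9% = 10.8 points. That needs invented rates. If the physicians' failure rates were 30% and 8%, the shift would be 0.22 × 12.1 = 2.7 points at 1 SE and 5.3 at 2 SE. No failure rate by physician is reported, and the assumed 22-point gap is twice the arm difference it is meant to explain. Even then the shift is only 0.29 to 0.58 of the failure difference's own SE of about 9.2 points. The failure and log-rank results are already non-significant, and nothing shows that adjustment would alter a conclusion.

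A third is that each physician measured IOP and decided on failure. This is a fair inference from one physician doing all of a patient's follow-ups, but the text says neither. Likewise, the absence of stratification by physician is inferred from a sentence about prior characteristics. A constant tonometry offset would also cancel, because outcomes are changes from pretreatment IOP, provided the same physician took both readings.

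Table 1 is not in the text available, so it cannot be said to omit physician.

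What remains is narrower: a correct average error rate does not tell a reader whether this one randomisation was balanced.

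**Conclusion.** The point holds as a minor, inexpensive improvement. The described comparisons carry no physician term although two unmasked physicians each treated and followed their own patients under unstratified allocation. The overall error rate of the unadjusted t-test is sound. The cost is a small loss of precision and, conditional on both a real physician difference and an uneven split, the shift shown in step 3. That size rests on an SD back-solved from the power statement and on assumed physician effects and shares. The actual adjusted result cannot be computed without data by physician.

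The more serious weakness nearby, unmasked follow-up with no stated criteria for further treatment, is separate. A physician covariate does not repair it. Nor does a main-effect term capture an arm-by-physician interaction, such as might arise if only the titrated laser varied by operator.

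**What to change.** - Analyse IOP change with a linear model on arm and physician (two levels). Show it beside the reported t-tests, and say that it was added after results were known.
- Report the number of patients by physician and arm. This table alone may settle whether imbalance is an issue.
- Report a physician-stratified log-rank test and a Mantel–Haenszel comparison of failure as sensitivity analyses only.
- State who measured IOP and who decided on further treatment.

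Cost: one degree of freedom in the linear model, under 1% of the SE if the physicians are alike, and a few lines of analysis, provided treating physician was recorded. No change to trial conduct is needed. The stratified failure comparison will be imprecise with about 13 failures (9 + 4) spread over two physicians and two arms, and should be read that way.

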## Results

There was no statistically significant difference in demographic characteristics between groups, as seen in Table 1. The MLT patients had a higher average starting IOP (18.26 mmHg) than the SLT group (16.85 mmHg), approaching significance (P=0.08). Both groups had very similar 1 hour posttreatment IOP, 15.15 mmHg in the MLT group and 15.65 mmHg in the SLT group. An IOP spike was defined as an elevation of .5 mmHg from the pretreatment mean. Incidence of post-procedure spikes were 5.3% and 12.9% in the MLT and SLT groups, respectively, but this difference was not statistically significant (P=0.4). No group experienced any anterior chamber inflammation upon examination at the 1 week follow-up time point.

Follow-up data at the 1-, 1–6-, 6–12-, 12–24-, 24–36-, and 36–52-week intervals were tabulated as absolute IOP decreases from pretreatment levels (Figure 1) and percentage IOP decreases from baseline (Figure 2). These data demonstrated that both MLT and SLT provided comparable decreases in IOP from baseline as both an absolute measurement and a percentage decrease at all intervals up 52 weeks (*P*.0.05). In addition, the confidence intervals at each time period were, 3 mmHg when viewed as an absolute decrease in IOP and, 20.0% when viewed as a percentage decrease from baseline IOP, except one outlier interval (week 24–36 in Figure 1). A Kaplan–Meier curve is demonstrated in Figure 3. As expected, the larger proportion of failures in the MLT group produced a lower curve, with more of the MLT failures occurring in the early period. However, the survival curve steps in both groups were similar at later intervals, leading to a log-rank *P*-value of 0.31.

The data from the standardized pain survey (scale of 0= none to 10= severe) revealed that the MLT patients experienced a mean 1.34/10 during treatment and 0.89/10 during the 1 week posttreatment period, while the SLT patients noted 2.83/10 during treatment and 2.81/10 during the 1 week posttreatment period. The MLT patients on average experienced less pain both during and after the treatment (P=0.005).

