Prior authors defined a successful laser trabeculoplasty as \$3 mmHg IOP decrease or \$20.0% IOP decrease from baseline.6,8 Using these criteria, 29.6% of the MLT and 36.0% of the SLT patients experienced a 20.0% IOP decrease from baseline during the 24–52-week interval (P=0.77). Similarly, 37.0% of the MLT patients and 36.0% of the SLT patients experienced a \$3 mmHg IOP reduction from baseline at the 24–52-week interval (P=1.0).

Patients in each group were also assessed to determine the proportion that required further intervention for their glaucoma during the 52-week follow-up period, indicating a failure of the laser therapy. In the MLT group, a total of 23.7% of patients failed and required further treatment for their glaucoma. A topical antiglaucoma agent was added in 15.8% of the MLT patients, incisional glaucoma surgery was performed in 2.6% of the MLT patients, and transscleral cyclophotocoagulation was performed in 5.3% of the MLT patients. In the SLT group, 12.9% of the patients failed, with all the failures due to the addition of another topical antiglaucoma medication. Although there were a greater number of failures in the MLT group (23.7%) compared to the SLT group (12.9%), the analysis did not meet significance in each individual category or when considered in sum (P=0.22). No patient in either group experienced any complications, other than a transient rise in IOP.

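### The 2.99 mmHg between-arm level is derived from a per-patient, from-baseline success criterion, so non-significant P-values do not demonstrate comparable IOP decreases

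*Combined protocol and SAP*

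**What the plan says.** The section headed Study Protocol and Statistical Analysis Plan with Results says that recruitment ended once a power analysis gave 80% power at a 0.05 level for "detecting an average 2.99 mmHg or 16.19% decrease from baseline between the SLT and MLT groups". On the origin of the figure it says: "This level was determined based on prior studies defining a" drop of 3 mmHg, or a "20.0% decrease in IOP as a significant difference from baseline". The same section names Student's t-test and Fisher's exact test for group comparisons. It states no equivalence or non-inferiority hypothesis and no between-arm margin.

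The Results conclude: "These data demonstrated that both MLT and SLT provided comparable decreases in IOP from baseline", on both the absolute and the percentage scale, with P above 0.05 at every interval. They add that the confidence intervals lay within 3 mmHg and 20.0%, "except one outlier interval (week 24–36 in Figure 1", which is the absolute scale. No exception is stated on the percentage scale.

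Later the Results use the same two thresholds for individual patients: "Prior authors defined a successful laser trabeculoplasty as" a decrease of 3 mmHg or 20.0%. For 24–52 weeks they report that "37.0% of the MLT patients and 36.0% of the SLT patients experienced a" 3 mmHg reduction.

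**The concern.** A threshold for one eye's whole change after treatment has been used as the gap to be detected between two active treatments. These are different quantities. A difference between lasers that matters would normally be only a part of what either laser achieves. A study sized to detect a gap as large as the full success criterion has little chance of detecting smaller gaps, so it will often return P above 0.05 when they exist.

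Comparability is the main efficacy conclusion and it is worded as demonstrated. If it rests on non-significance, it claims more than the design can give. If 2.99 mmHg was instead meant as a decrease within an arm, the 80% says nothing about a difference between arms, and the conclusion is no better supported.

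**Working it through.** **Inputs.** From the power statement: 80% power, 0.05 level, 2.99 mmHg or 16.19%, with 38 MLT and 31 SLT randomized. From the Results, at 24–52 weeks: 29.6% and 36.0% reached 20.0% (P=0.77), and 37.0% and 36.0% reached 3 mmHg (P=1.0). The SD of IOP change, the n behind the 80% and its sidedness are not given, so the 80% cannot be reproduced forward. I take it as stated and assume a two-sided test.

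**1. What 80% at 2.99 mmHg implies.** Under the normal approximation, difference = (z₀.₉₇₅ + z₀.₈₀) × SE.
- SE = 2.99 / (1.960 + 0.842) = 1.067 mmHg. Neither n nor SD enters.
- 95% CI half-width = 1.960 × 1.067 = 2.09 mmHg (2.10 with t quantiles at 38 v 31 or 27 v 25).
- Check: power at 2.99 = Φ(2.99/1.067 − 1.960) = 80%, as stated.
- On the percentage scale: SE = 16.19 / 2.802 = 5.78 points, half-width 11.3 points.
- If the 80% were one-sided, SE = 2.99 / (1.645 + 0.842) = 1.20 mmHg and the half-width would be larger, 2.36 mmHg.

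**2. Power for smaller true gaps**, Φ(gap/1.067 − 1.960):

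| True gap (mmHg) | Power |
|---|---|
| 1.0 | 15% |
| 1.5 | 29% |
| 2.0 | 47% |
| 2.99 | 80% |

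A result that just misses significance has a 95% CI reaching 2 × 2.09 = 4.2 mmHg.

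**3. Margins that could be met.** To lie within a margin M, the CI needs an observed gap below M − 2.09. For M below about 2.1 mmHg this is impossible even with an observed gap of zero. For M = 3 mmHg it needs an observed gap below 3 − 2.09 = 0.91 mmHg.

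**4. Late responders.** The counts are inferred, not printed. Up to 38, only a denominator of 27 gives both 29.6% (8) and 37.0% (10). Up to 31, only 25 gives 36.0% (9). Two-sided Fisher P for 8/27 v 9/25 is 0.769, and for 10/27 v 9/25 it is 1.0. Both match the report.

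Not reaching 3 mmHg: 17/27 = 63.0% and 16/25 = 64.0%. With more than half below 3 mmHg in each arm, both observed medians are below 3 mmHg. No SD or normality is needed. This describes analysed patients only, because responses after a further intervention are excluded.

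**5. Between-arm responder differences, MLT minus SLT (Newcombe 95% CI).** Wilson limits are 21.5–55.8% for 10/27, 15.9–48.5% for 8/27 and 20.2–55.5% for 9/25. Lower limit = d − √[(p₁−l₁)² + (u₂−p₂)²]; upper limit = d + √[(u₁−p₁)² + (p₂−l₂)²].
- 3 mmHg: d = 0.370 − 0.360 = +1.0 point. Lower: 0.010 − √(0.155² + 0.195²) = −0.239. Upper: 0.010 + √(0.187² + 0.158²) = +0.255. CI −24 to +26 points.
- 20.0%: d = 0.296 − 0.360 = −6.4 points. Lower: −0.064 − √(0.138² + 0.195²) = −0.302. Upper: −0.064 + √(0.189² + 0.158²) = +0.182. CI −30 to +18 points.

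Against an SLT rate of 36.0%, the lower limits allow MLT to fall short by about two thirds (24/36) and five sixths (30/36) of that rate.

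**The case against.** The strongest reply is that similarity is judged from observed differences and their confidence intervals, not from prior power, and that the Results do make such a check. By their account all intervals on the percentage scale, and all but one on the absolute scale, passed, and the exception is openly disclosed. This stands in part. The check is the only equivalence-type evidence offered, and it should not be reduced to its one exception. But it reuses the same 3 mmHg and 20.0% levels, the text does not say whether the intervals are per arm or between arms, and the limits are in figures not available here.

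A reader might infer that no sample size could make this trial support comparability. That does not follow. The bar is absolute only for margins below about 2.1 mmHg; a 3 mmHg margin could be met with an observed gap under about 0.91 mmHg.

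A reader might also infer that 2.99 mmHg exceeds the whole late effect, so that even complete loss of effect in one arm would go undetected. The documents do not support this either. The power statement concerns an average, only the medians can be bounded from the text, and the late means are in the figures. The pooled responder rate of 19/52 has an upper 95% limit of 51%. With normal changes that allows a mean decrease of about 3.1 mmHg. Power to detect complete loss would then be 71–91% at 27 v 25 and 83–97% at 38 v 31. This is for an assumed SD of 4.35 (80% power on all 69 patients) down to 3.28 (implied by the baseline P of 0.08, so not an SD of change).

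The documents never use the terms equivalence or non-inferiority, and the late responder data do not speak to the earlier intervals. Both are true, but saying that comparability was demonstrated is still a claim of similarity.

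**Conclusion.** The concern holds in limited form. The between-arm level was taken from a from-baseline, per-patient criterion, and fewer than 40% of analysed patients in either arm met its 3 mmHg version at 24–52 weeks. With the stated 80% taken as two-sided, the study had less than even power for a true gap of 2 mmHg and about 15% for 1 mmHg. Late responder differences are compatible with anything from −24 to +26 points (3 mmHg) and −30 to +18 points (20.0%). The data support a statement that no significant difference was found. They do not demonstrate comparability, because no between-arm margin is stated or justified.

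This rests on the normal approximation, on taking the 80% at face value, and on responder counts inferred from percentages. The 80% is unverifiable from the text; it is not shown to be wrong. Nor is it shown that the lasers differ.

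**What to change.** 1. In the power paragraph, state that 3 mmHg or 20.0% is a per-patient, from-baseline criterion, and stop giving it as the reason for the between-arm level.
2. In the Results, replace the sentence claiming demonstrated comparability with: *No significant difference was found; the study was not designed to show equivalence or non-inferiority.*
3. Add one table giving, for each interval, the between-arm difference with 95% CI and n per arm, on the absolute and percentage scales. Say explicitly that the intervals are between arms. Print the late responder counts.
4. If comparability is still to be claimed, judge those intervals against a between-arm margin justified as a part of the SLT effect, and say that a margin chosen now is post hoc.

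The cost is a few sentences and one table from data already held. No new patients are needed. The conclusion becomes weaker.

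### Patients who needed further glaucoma treatment before week 24 drop out of the 24–52-week success rates instead of counting as non-responders, and those rates cover only 27 of 38 MLT and 25 of 31 SLT patients

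*Combined protocol and SAP*

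**What the plan says.** The methods text (section Study Protocol and Statistical Analysis Plan with Results) states that patients' "responses were excluded from the analysis if they underwent any interventions that may affect their IOP". Its list covers an added pressure-lowering drop, cataract surgery, cyclophotocoagulation, incisional glaucoma surgery and repeat laser trabeculoplasty. It continues: "However, their data were still included for the intervals up to the time of these interventions". No rule says how such a patient is scored in a responder analysis.

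The Results give success on two criteria for weeks 24–52. For the 20% criterion, "29.6% of the MLT and 36.0% of the SLT patients experienced a 20.0% IOP decrease from baseline" (P=0.77). For a fall of at least 3 mmHg, "37.0% of the MLT patients and 36.0% of the SLT patients experienced a" success (P=1.0). The text gives no numerators or denominators for these rates.

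The Results also count patients who "required further intervention for their glaucoma during the 52-week follow-up period, indicating a failure of the laser therapy". For MLT: "In the MLT group, a total of 23.7% of patients failed and required further treatment for their glaucoma". The SLT figure is 12.9%. On the Kaplan–Meier curve the text says that "the larger proportion of failures in the MLT group produced a lower curve", "with more of the MLT failures occurring in the early period".

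**The concern.** The two parts of the document treat the same event differently. An added drop, cyclophotocoagulation or incisional surgery is a laser failure in one analysis and a reason for removal in the other. A patient who had one of these before week 24 contributes no 24–52-week pressure and so leaves both the numerator and the denominator of the success rate. Leaving a known failure out makes the rate among those who remain higher than it would be with that failure counted.

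The rates are worded as percentages of the MLT and SLT patients, so a reader will take them as results for the randomised groups. They also stand beside failure rates that do use all randomised patients, and the text gives no notice that the base has changed.

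**Working it through.** **Inputs.** Randomised: 38 MLT, 31 SLT (methods). Success rates 29.6%, 37.0% and 36.0% (the last for SLT on both criteria), P=0.77 and P=1.0; failure rates 23.7% and 12.9% (Results). Test: two-tailed Fisher's exact (methods).

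**Step 1: recover the counts.** I listed every fraction x/n with n up to 38 (MLT) or 31 (SLT) that rounds to the printed percentage. Each has one solution:

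| Printed | Only fit |
|---|---|
| MLT 20% criterion, 29.6% | 8/27 |
| MLT 3 mmHg criterion, 37.0% | 10/27 |
| SLT both criteria, 36.0% | 9/25 |
| MLT failures, 23.7% | 9/38 |
| SLT failures, 12.9% | 4/31 |

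**Step 2: reproduce the printed P values.** Two-sided Fisher gives 0.769 for 8/27 vs 9/25 (printed 0.77) and 1.0 for 10/27 vs 9/25 (printed 1.0). The counts are therefore secure.

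**Step 3: who is absent.** 38 − 27 = 11 MLT patients and 31 − 25 = 6 SLT patients. Reported failures number 9 and 4, so at least 11 − 9 = 2 and 6 − 4 = 2 absentees are not reported failures. These could be cataract-surgery exclusions, which are not among the reported failures, or missed visits. The text does not say how many of the 9 and 4 failures came before week 24.

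**Step 4: effect of the exclusion rule over the unknown split.** Let k failures be absent. Score them as non-responders, assume that other absentees respond at the included rate r, and recode no included responder. The all-randomised rate is r × (N − k)/N, a fall of r × k/N.

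| | Fall per absent failure | Range, k from none to all |
|---|---|---|
| MLT, 3 mmHg | (10/27)/38 = 0.97 points | 0 to 8.8 (k = 9) |
| MLT, 20% | (8/27)/38 = 0.78 points | 0 to 7.0 (k = 9) |
| SLT, either | (9/25)/31 = 1.16 points | 0 to 4.6 (k = 4) |

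**Step 5: add only the failures, if all were absent.** Denominators become 27 + 9 = 36 and 25 + 4 = 29. Differences are MLT minus SLT, with Newcombe 95% CI and two-sided Fisher P.

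| | MLT | SLT | Difference, points (95% CI) | P |
|---|---|---|---|---|
| 3 mmHg, as printed | 10/27 = 37.0% | 9/25 = 36.0% | +1.0 (−23.9 to 25.5) | 1.0 |
| 3 mmHg, failures added | 10/36 = 27.8% | 9/29 = 31.0% | −3.3 (−25.0 to 18.0) | 0.79 |
| 20%, as printed | 8/27 = 29.6% | 9/25 = 36.0% | −6.4 (−30.2 to 18.2) | 0.77 |
| 20%, failures added | 8/36 = 22.2% | 9/29 = 31.0% | −8.8 (−29.8 to 12.2) | 0.57 |

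Adding any number of absent failures from 0 to 9 (MLT) and 0 to 4 (SLT), the smallest P is 0.26 (20%) and 0.58 (3 mmHg).

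**Step 6: missing-data bounds, which are not the effect of the rule.** With every absentee a non-responder, the rates are 10/38 = 26.3% vs 9/31 = 29.0% (P=1.0) and 8/38 = 21.1% vs 9/31 = 29.0% (P=0.58). In the other direction, 6 absent MLT failures with the other 5 absentees all responding gives 15/38 = 39.5% on 3 mmHg, above the printed 37.0%. With no failure absent and every absentee responding, the ceilings are 21/38 = 55.3% and 19/38 = 50.0% (MLT) and 15/31 = 48.4% (SLT).

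**The case against.** The strongest defence is that the rule is stated openly and answers a legitimate question: pressure response without further treatment. Further intervention is reported separately over all randomised patients, with a Kaplan–Meier curve and a log-rank test. Two outcomes may have two denominators, and a composite that scores intervention as non-response is one reasonable choice among others. This stands in part. The failures are disclosed, and the existing rates are usable if labelled for what they are. But separate disclosure does not tell the reader that 17 of 69 patients are missing from the success rates, or how many of the 17 are failures.

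The size is also uncertain, and three stronger readings should be resisted.

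- A reader might infer that the absentees are essentially the failures. At least 2 per arm are not reported failures, and a patient who failed within weeks 24–52 could still be among the 27 or 25 through earlier data in that window.
- A reader might take the drop to 26.3% and 21.1% (MLT) and 29.0% (SLT) as the cost of the exclusion rule. Those figures would be the same if no failure had been excluded; they reflect an assumption about all missing patients.
- A reader might conclude that corrected rates must be lower, or that the rule favours MLT. Step 6 shows that the rates could rise if few absentees are failures and the others responded. More MLT failures, more of them early, make a larger effect in MLT plausible. But the early period is not defined against week 24, and the imbalances are compatible with chance (failures 9/38 vs 4/31, Fisher P=0.36; absentees 11/38 vs 6/31, P=0.41). The Results print 0.22 for the failure comparison, also non-significant.

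The tables and figures were not available to this review, so the remark on missing denominators applies to the text only.

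**Conclusion.** The point holds as a fault in how failures enter the success rates and in how those rates are labelled. It does not change the trial's conclusion. It is certain that the printed rates rest on 27 and 25 patients, and that the written rule removes anyone who failed before week 24. How many failures were removed is not known. The effect of the rule runs from nil to 8.8 points (MLT, 3 mmHg), 7.0 (MLT, 20%) and 4.6 (SLT), provided that other absentees respond at the included rate and no included responder is recoded as a failure. Each included responder who failed later in the window would take off a further 1/38 = 2.6 points (MLT) or 1/31 = 3.2 points (SLT).

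Every comparison above remains non-significant, and the change of sign on the 3 mmHg criterion is far inside its confidence interval. The success rates are not named as the primary outcome. This should be fixed, at modest priority, because the rates as printed cannot be read as results for the randomised groups.

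**What to change.** Report the 24–52-week responder analysis over all randomised patients (38 and 31), scoring further glaucoma intervention before or during the interval as non-response. Handle patients absent for other reasons, including cataract surgery, by a stated missing-data rule, with one sensitivity analysis under a second rule. State the denominators and how many of the 9 and 4 failures lie inside the 27 and 25. Give the MLT–SLT difference with a 95% CI. The existing rates may stay if labelled as response without further intervention among patients with data.

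The cost is some re-analysis of data already held and revised wording, with no new visits or patients. The success rates will probably be lower, though this is not guaranteed.
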